#### Specific aims and Research Hypotheses:

**Aim 1: To determine the impact of home-based NMES-RT protocol plus oral Vit D supplementation, compared to passive movement plus oral Vit D on bone micro-architectural properties, as measured by MRI in Veterans with chronic SCI (> 1 year post SCI).** Both groups will receive 9 mos of prescribed treatment. We hypothesize that NMES-RT+ Vit D supplementation will result in improved trabecular bone parameters after SCI. We plan to compare changes in bone composition including bone marrow fat (MBF) and cortical porosity, at the distal femur and proximal tibia, as measured by MRI and DXA in the two groups, at enrollment and end of intervention (9 mos). We will analyze the effect of Vit D based on levels of 25-(OH)D, at enrollment; mid-intervention (4.5 mos), and at 9 mos. Participants with > 40ng/mL of 25 (OH)D will be excluded from the study.

**Hypothesis:** NMES-RT+ Vit D supplementation will result in improvement in trabecular and cortical bone parameters compared to passive movement and Vit D supplementation after 9 months in persons with SCI.

**Aim 2: To determine the impact of home-based NMES-RT protocol plus oral Vit D compared to passive movement and Vit D supplementation on biomarkers of bone formation and bone resorption in Veterans > 1-year post SCI.** Both groups will also receive 9 months of therapy. We hypothesized that NMES-RT will increase osteoblast activity and decrease bone demineralization compared to passive movements. We plan to measure serum 25(OH)D, PTH, Bone specific alkaline phosphatase ( BALP), Procollagen Type 1 Intact N Terminal Propeptide (P1NP), Hydroxyproline (HYP), Carboxy-terminal Crosslinked Telopeptide of Type 1 collagen (CTX), in participants' blood. The role of bone turnover markers in the evaluation of bone loss in persons with SCI has not been established. In able-bodied persons, serum CTX and serum P1NP are considered the best markers of bone resorption and formation, respectively. Blood analysis will be done at enrollment, 4.5 mos and 9 mos, for both groups. We plan to account for dietary intakes of protein, sodium, calcium, and phosphorous on BMD. Each participant will turn in dietary logs of 3-days per week on a weekly basis. The dietary log of each participant will be analyzed by our registered dietitian using Nutrition Data System for Research (NDSR) software. We will solicit the service of our dietitian who will contact participants once a month to advise them on balanced diet. Additionally, the World Health Organization quality of life (WHO-QOL) survey will be used to assess participants' physical and mental domains after intervention. The WHO-QOL is a survey instrument that rates six broad domains on health (physical, psychological, level of independence, social relations, environment, and spirituality/religion/personal belief), using a five-point Likert scale (1-5) to produce a total of 100 items in assessment. This survey will be administered at enrollment and at the end of intervention. It takes about 15 minutes to complete the survey. Data obtained from the survey will serve as preliminary data to determine whether exercise programs could also enhance the QOL for persons with SCI. It will be interesting to note any association between physical domain and bone parameters after SCI.

**Hypothesis: Osteoblastic and osteoclastic activities undergo obvious dynamic changes favoring bone loss after SCI.** NMES-RT +Vit D supplementation increases osteoblastic activity and decreases bone demineralization as observed by decreased biomarkers of osteoclastic activity compared to passive movement and Vit D supplementation.

**Subjects:** Twenty Veterans and non-Veterans with >1 year of SCI will be recruited from CVHCS and (VCU, if insufficient Veteran participants). The CVHCS SCI registry has ~1,800 Veterans and more than 298 meet the inclusion criteria of C8-T10 level of injury.

**Inclusion Criteria:** Participants should be 18-65 years of age; male or female, with traumatic motor complete SCI ( $\geq$ 1-year) and C8 to T10 neurological level of injury (NLI), by the International Standards for Neurological Classification (ISNCSCI) of SCI, serum 25(OH)D  $<$  41ng/mL, be a wheelchair user for primary mobility, be able to receive written clearance from their medical Providers to ensure safety of participants, accessible caregiver capable of physically supporting participant throughout the trial and willing to be trained to apply intervention protocol in the home (placing weights and positioning the Veteran) throughout study duration, and have normal ECG. Participants' knee extensors must respond to standard surface NMES procedures (frequency: 30 Hz; pulse duration:450  $\mu$ s and amplitude of the current  $<$  200 mA), to ensure intact neural circuitry below the level of SCI. All participants will undergo NLI examination. Only those with American Spinal Cord Injury Impairment Scale (AIS) **A and B** will be included. Age limit of 65 years is to avoid cardiovascular challenges that could be provoked by 9 months of strenuous physical activity in older persons. Moreover, persons older than 65, have more than 2-fold risk of osteoporosis related fractures, which may confound the trial.

**Exclusion Criteria:** Participants with any of the following pre-existing medical conditions will be excluded from the trial: **1)** neurological injury other than SCI,(e.g. cauda equina or distal conus injuries resulting in limb or sacral areflexia; **2)** Unhealed fracture in either lower or upper extremities; **3)** Severe scoliosis, hip knee range of motion (ROM)  $>$  20 degrees. or flexion knee contractures **4)** Uncontrolled hypertension (BP  $>$ 140/90 mmHg) and severe orthostatic hypotension (BP drop  $>$  20 mmHg) or inability to maintain a sitting position ; **5)** Other medical conditions like cardiovascular disease, uncontrolled type II DM, insulin-dependent DM, or symptomatic urinary tract infection; **6)** severe hypercalcemia (defined as Serum calcium  $>$ 16 ng/mL); **7)** anti-coagulant or anti-platelet therapy, including aspirin. **8)** pacemakers and/or defibrillator devices in place, metallic implants, shrapnel or bullets in the vertebral column, or other contraindications for MRI; **9)** DXA total body-score  $<$  -2.5, knee BMD scores  $<$  0.6 g/cm^2; **10)** Participants with spasticity that is severe or adjudged a contraindication by the site Physician or limited ROM will be excluded. **11)** Pressure ulcer of the trunk, pelvic area, or lower extremities of  $\geq$  stage 3; **12)** Psychopathology history that may conflict with study objectives; **13)** Potential participants who are not wheelchair users and cannot transfer with sliding boards or portable lifts.**14)** serum Vit. D  $>$  40 ng/mL; **15)** abnormal/elevated calcium level **16)** pregnancy (female participants). Medically accepted birth control is required to enter this study. This may include, but is not limited to, birth control pills, IUD's, condoms, diaphragms, implants, being surgically sterile, or being in a post-menopausal state. A blood pregnancy test will be conducted to rule out any pregnancy before the study at the McGuire VAMC. The test will be repeated every month during the course of the study. The blood samples will be sent to the McGuire VA pathology lab for analysis. **17)** Any condition that, in the judgment of the principal

investigator or medical provider precludes safe participation in the study and/or increases the risk of infection. A large percentage of patients in the department of VA are males. Should female participants be found, in order to ensure heterogeneity of samples between the two groups, postmenopausal and estrogen deficient females and men undergoing anti-androgen therapy or post orchiectomy, will be excluded. In addition, individuals with stage 3b or higher chronic kidney disease and those likely to have bone loss (age >65), will be excluded due to possible renal osteodystrophy and osteoporosis that may increase the risk of bone fractures from bone loading and ES to muscles. We will also exclude those with AIS C & D as they are already engaging in weight bearing activities which may confound the results of the trial. We have chosen inclusion and exclusion criteria for this study, to optimize homogeneity. Should the outcome be positive, it will be necessary to broaden inclusion criteria for future studies so that the methods can be used in a larger number of individuals with SCI.

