#### **Passive range of motion or passive stretching:**

Participants assigned to the passive exercise and Vitamin D group will have their caregivers perform passive ROM. Caregivers will be instructed to sit on a stool, cup the participant's leg above the ankle joint, and move it from 90-degrees of knee flexion to full knee extension. The leg will be maintained in extension for 5 sec and returned to flexion for 5 sec. The passive actions are repeated in the manner described in the RT protocol; 10 reps on the right leg followed by 10 reps on the left leg for 4 sets x 10 reps. This exercise training will take place twice a week. Each training exercise will last 30 – 40 minutes each day of the exercise.

**Blood Pressure (BP) Monitoring:** The caregiver will measure the participant's BP before starting the exercise, record the reading and leave the BP cuff in place. About 15 to 20 minutes into the exercise, another BP reading will be taken and the final reading at the end of the exercise to safeguard against Autonomic Dysreflexia (AD). Most individuals with high cervical and thoracic levels of SCI own BP machines. However, if they do not own one, they are eligible to get one from their Providers.

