**Resistance training (RT):** Participants and caregivers will be trained on RT (application of electrodes, initiating and adjusting currents and the application of ankle weights). Resistant Training will be performed twice weekly **in an open-chain format (resistance is placed at the distal part of an extremity in a fixed position) in the first 4.5 mos, followed by 4.5 mos in a closed-chain format using surface NMES.** Initial open-chain format ensures muscle hypertrophy that is likely to cause modest bone adaptations, prior to it being subjected to significant loading during closed-chain format. This would ensure bone safety during the close kinematic exercise. No ankle weights in the first week to ensure full knee extension against gravity. Weekly increments of 2 lbs. will be used on the condition that full knee extension is achieved before any increase in load. NMES of the extensor muscles of the knee, for concentric-eccentric actions will be by surface electrodes as shown in **fig 1**. Two 8 X10 cm^2 (Uni-Patch, Wabasha, MI, USA) adhesive carbon electrodes will be placed on the skin over the knee extensor muscle group. Current from the stimulator will be increased at 5-second intervals to evoke full knee extension against gravity followed by the lengthening action during relaxation. The current (mA) that causes full knee extension will be recorded. Training will be performed remotely, twice weekly for 4 sets of 10 repetitions under full supervision from the PI **by telehealth**. Each RT session will consist of 4 sets of 10 repetitions of NMES-induced knee extensions for 60 min. A 5 sec/5 sec work/rest ratio will be used with 3 min rests between sets, 30 Hz, 1 ms pulses and current

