**Inclusion of women Veterans:**

There is inherently gender disparity in the Veteran population based on the fact that more men than women tend to join the military. However, the study team will make every effort to recruit female Veterans but may be limited due to scarcity of female Veterans with SCI.

**Exclusion criteria:** Every effort will be made to ensure participants' safety and any participant with active medical condition that may confound the result of the trial will be excluded from participation.

Potential participants will be excluded if they exhibit any of the following:

1. Neurological injury other than SCI
2. Older than 65 years of age as they may likely have considerable amount of bone loss at that age.
3. Have severe osteoporosis because loading porous/fragile bone by electrical stimulation may result in bone fracture.
4. Those classified as AIS C & D, as they may already be engaging in weight bearing activities that may confound the results of this trial.
5. Unhealed or unstable fractures in either lower or upper extremities.
6. Severe scoliosis, deformities in the hip, knee, or ankles OR impaired range-of-motion, as these could be a barrier to safe positioning on the rowing machine, and on MRI or DXA tables.
7. No caregiver or family member/significant other, willing to help with placing weights and positioning participants' lower extremities on the rowing machine.

8. Untreated or uncontrolled hypertension (systolic blood pressure (BP) > 140 mmHg; diastolic BP > 90 mmHg), and/or sudden hypotension upon transferring from bed to wheelchair, characterized by a drop in BP by 20 mmHg (especially in persons with tetraplegia) or heart rate > 100 beats per minute.
9. Anti-coagulation or anti-platelet therapy (including aspirin)
10. Implanted pacemakers, implanted defibrillator devices or any metallic implants including knee or hip implants.
11. Presence of bullets in vertebral column or shrapnel anywhere in the body that may interfere with MRI procedure.
12. Other medical conditions including cardiovascular disease, uncontrolled type II DM, active deep vein thrombosis (DVT), uncontrolled autonomic dysreflexia, use of insulin for DM management, pressures injuries of stage 3 or higher, or active urinary tract infection.
13. Severe hypercalcemia (serum calcium > 16mg/dl), stage III-V kidney disease, post-menopausal or estrogen dependent female, and men undergoing anti-androgen therapy or are post orchiectomy.

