### **Protection Against Risk:**

Every effort will be made by the PI and the study team to minimize potential risks. Any procedures will be carried out in accordance with established standard operating procedures and necessary precautions will be taken to mitigate any potential risk. There will be strict adherence to the inclusion & exclusion criteria for the protocol. Appropriate

health screening and strict compliance with the established exclusion criteria will minimize attrition due to medical reasons. Participants will be closely monitored by the PI at all visits. All participants will be provided a 24-hour contact information for the PI and instructed to call for any concerns. Unscheduled visits may be performed if required for evaluation of safety. If a participant exhibits an adverse event, more frequent visits may be necessary.

- Protection of skin integrity during intervention

Skin will be closely inspected with the help of the caregivers for dose with caregivers, otherwise, by the PI via the webcam during each intervention session to ensure maintenance of skin integrity.

- Protection from risk associated with transfers

To minimize risk, a caregiver will be available to assist in all transfers and provide a sliding board or any other assistive devices needed for those without good upper body strengths. For those without caregivers, safe transfer techniques would have been validated prior to enrollment.

- Protection from risk associated with radiation exposure

To minimize risk, only the required scans will be performed. Testing will be performed early in the day and after lower extremity elevation for at least 30 minutes to minimize lower extremity edema. An overhead lift system is installed in the exercise lab to ensure safe transfers on and off the DXA scanner.

A possible health problem seen with radiation exposure is the development of cancer later in life. This extra cancer risk is higher at younger ages and for girls and women. The extra lifetime risk of dying of a fatal cancer due to the radiation exposure from this research is very low. At such low radiation exposures, scientists disagree about the amount of risk. These estimates are very uncertain, and there may be no extra risk at all.

- Protection from falls during transfers

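### Exclusion item 3 bars hip/knee range of motion above 20 degrees, which cannot be what was meant and leaves the eligibility rules without a usable motion limit

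*Combined protocol and SAP*

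**What the plan says.** The protocol has two exclusion lists, and joint motion appears in three of their items.

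- **Research Design and Methods, Exclusion Criteria, item 3.** It begins "Severe scoliosis, hip knee range of motion (ROM", followed by a greater-than sign and "20 degrees. or flexion knee contractures". A hip or knee range of motion above 20 degrees is thus printed as a reason to exclude.
- **Same list, item 10.** Besides severe spasticity, it covers spasticity "adjudged a contraindication by the site Physician or limited ROM will be excluded". Here too little motion excludes, and no figure is given.
- **Human Subject Section, Exclusion criteria, item 6.** It excludes deformities of the hip, knee or ankles, or "impaired range-of-motion, as these could be a barrier to safe positioning on the rowing machine" and on the imaging tables. Again too little motion excludes, with no figure.

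The exercise sections show what motion is needed. In the control arm, both descriptions of passive range of motion have the caregiver take the leg and "move it from 90-degrees of knee flexion to full knee extension". In the stimulation arm, the Resistance training (RT) section allows weekly weight increases only "on the condition that full knee extension is achieved before any increase in load". The earlier Resistance training and Rowing Exercise section also requires full extension from a seated position.

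Under Protection Against Risk the protocol states: "There will be strict adherence to the inclusion & exclusion criteria for the protocol".

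**The concern.** Item 3 excludes people for having motion, while the other two items exclude people for lacking it. The three cannot all be applied as printed, and item 3 also conflicts with the movement that the trial asks participants to perform.

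The item is operative. Range of motion is part of the musculoskeletal screening examination in the Human Subject Section, and eligibility is to be based on the examination findings. The second list gives a safety reason for the motion exclusion, namely positioning on the rowing machine. Files are to be reviewed regularly for protocol violations, and the monitoring board's letter is to cover adherence. With item 3 as it stands, neither the screening physician nor the board has a written standard for deciding whether a participant with some loss of hip or knee motion was correctly enrolled.

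**Working it through.** The plan has no calculated figure on this point to reproduce. The check compares the printed rule with the other passages.

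**Inputs**

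1. Item 3 threshold: exclude if hip/knee range of motion > 20 degrees (Exclusion Criteria, Research Design and Methods).
2. Item 10 of the same list: exclude if motion is limited, no number.
3. Item 6 of the Human Subject Section list: exclude if motion is impaired, no number.
4. Control exercise: knee moves from 90 degrees of flexion to full extension, an arc of about 90 degrees.
5. Stimulation arm: full knee extension, starting seated in a wheelchair. No starting angle is stated.

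**Step 1: literal reading.** A participant who can complete the control movement has a knee arc of about 90 degrees. Since 90 > 20, that participant meets the item 3 exclusion. A participant with an arc of 20 degrees or less escapes item 3 but has at most 20/90 = 22% of the required arc, and so falls under limited motion in item 10. Taken together and literally, items 3 and 10 admit no one who can do the control exercise.

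**Step 2: is the sign a text-extraction fault?** Other inequalities in the same list run in the expected direction: blood pressure above 140/90 mmHg, a pressure drop above 20 mmHg, vitamin D above 40 ng/mL, knee bone density below 0.6 g/cm². A corrupted sign in this one place is unlikely.

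**Step 3: can the intended rule be recovered?** Two repairs suggest themselves.

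- *The sign is reversed.* Item 3 would then exclude motion below 20 degrees. A knee with a 25-degree arc would pass item 3, yet 25 is far short of 90 and the movement could not be done. Only the unquantified item 10 would catch this person.
- *A word such as deficit or limitation is missing.* Item 3 would then exclude a loss of more than 20 degrees. A knee with a loss of exactly 20 degrees would keep 90 − 20 = 70 degrees of the arc and pass the numeric part. If the loss were in extension, that person could not reach the full extension on which weight increases depend. The phrase on knee flexion contractures, which carries no number, might also exclude the same person.

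The general intention, to exclude restricted motion, is clear from items 10 and 6. The rule is not. The text does not settle whether 20 degrees is an arc, a loss or a contracture angle, or whether it applies to the hip, the knee or both. It also does not say whether any knee flexion contracture excludes. The exercise sections give no hip angle against which to test the figure. The second list adds the ankles, which item 3 does not mention.

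**Step 4: is there another limit to fall back on?** No. Item 3 holds the only numeric joint-motion limit in either list.

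**The case against.** The strongest reply is that this is a drafting slip which no screener would follow. Item 3 itself names contractures, item 10 names limited motion, the second list explains why impaired motion matters, and the exercises plainly need full extension. In that context nobody would be turned away for having normal joints. This stands. A reader might infer from Step 1 that almost no one is eligible, or that every participant able to train would be a violation. That describes the literal reading only and is not a forecast of what the site would do.

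A reader might also infer that the inequality is simply reversed. The documents do not show that. A missing word fits the broken clause at least as well, and the sign would then be correct.

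Nor does the text support a 90-degree requirement in both arms. It states the 90-degree start for the control arm only. For the stimulation arm it requires full extension from sitting.

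On safety, item 3 is not the only protection. There is also a screening examination that includes range of motion, bone-density exclusions, written clearance from medical providers, an investigator-judgement exclusion and the full-extension condition on adding weight. Wide variation between screeners is unlikely too, since this is a single-site pilot of 20 with screening by the investigator or an SCI specialist physician.

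What the objection does not remove is the defect itself. Common sense recovers the direction of the exclusion but not the quantity, the joint or the limit, and the protocol commits to applying its criteria strictly.

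**Conclusion.** Item 3 is wrong as written. It contradicts item 10 of its own list, item 6 of the second list and the movement required in the control exercise. It cannot be repaired by inference, because the plausible repairs lead to different rules. The practical consequence is an eligibility list with no usable numeric limit on joint motion. It is not an empty trial population or an unprotected one.

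The size of the problem cannot usefully be given as a percentage. The ratio of the 90-degree arc to the 20-degree figure shows only that the printed rule fails. It would not measure any effect on enrolment, because the 20 degrees may not refer to an arc at all. No endpoint, analysis or power statement depends on the item.

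The conclusion assumes that the greater-than sign is in the source document, which the other inequalities in the list support, and that the two exclusion lists are meant to apply together.

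**What to change.** Reconcile items 3 and 10 of the Exclusion Criteria in Research Design and Methods with item 6 of the Exclusion criteria in the Human Subject Section. Replace them with one measurable motion criterion, worded identically in both places, that states:

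- the quantity measured (arc, loss of motion or contracture angle);
- the joint or joints to which it applies;
- the direction in which it excludes;
- the limit, and whether a knee flexion contracture of any size excludes.

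The limit is a clinical decision for the sponsor's clinicians, and none is proposed here. They should check that it fits the movements described in the two exercise sections. The cost is one eligibility line in two places. No change to sample size, schedule or analysis follows. If anyone has already been screened, it would help to record how item 3 was applied.
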